4.1. Control Group

4.1.1. Summary: Received an autonomous preoperative rehabilitation exercise programme.

4.1.2. Method: On the day of admission, a research assistant provided a verbal explanation of the preoperative rehabilitation exercise regimen and distributed a guidance manual. Participants are advised to perform autonomous exercises 2–3 times daily according to the manual from admission day to surgery day (preoperative). They were also advised to promptly inform ward medical staff of any unusual conditions or concerns.

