4.2. Experimental Group

4.2.1. Summary: Received a patient-navigation-based preoperative rehabilitation exercise programme

4.2.2. Method: From admission day to surgery day (preoperative), navigator provided full-period preoperative rehabilitation exercise guidance and navigation services aimed at promoting rehabilitation exercise.

A. The navigator provided full-period preoperative rehabilitation exercise guidance, which displayed as follows: (The preoperative rehabilitation exercise regimen guided by the navigator was the same as that of the control group.)

- a) On the day of admission, in addition to explaining the preoperative exercise regimen and distributing a guidance manual as done for the control group, the navigator demonstrated the exercise movements and required participants to

perform return demonstrations to ensure mastery of the exercises.

- b) During the preoperative period, navigators conducted daily ward visits to provide face-to-face exercise guidance, including two 20-minute supervised sessions per day, and sent exercise reminder text messages every night from 7:00 PM to 8:00 PM.

B. The navigation services aimed at promoting rehabilitation exercise encompassed the following seven themes: On the day of admission, (i) establish contact with participants or their carers, and (ii) provide disease-related education. During the preoperative exercise period, (iii) assess participant needs and facilitate access to resources; (iv) offer social and emotional support; (v) provide verbal interpretation services

available upon request; (vi) identify and address barriers to exercise implementation; and (vii) support participants' self-management.

(i) Establish contact with participants or their carers: On the day of admission, the navigator will add the participant's or their carer's contact details and inform them that they may consult the navigator via these contact details should they have any queries or requirements during the preoperative rehabilitation exercise period.

(ii) Provide disease-related education:

- ① Knee Osteoarthritis Information: Including the definition of osteoarthritis, the development of knee osteoarthritis, and the grading of knee osteoarthritis.
- ② Total Knee Arthroplasty Surgery Information: Surgical method and benefits of the surgery.

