- ② Guidance for participants with underlying conditions: Upon admission, navigators conduct detailed assessments of participants' underlying conditions, collaborating with the medical team to develop personalised management plans. Participants receive instruction on monitoring relevant indicators and operating associated devices, adhering to medication schedules as prescribed, managing daily lifestyle factors (diet, exercise, weight control), and recognising and handling emergencies or abnormal symptoms.
- ③ Postoperative self-management guidance for TKA:
 - Wound care: Explain dressing change schedules, precautions during dressing changes, and wound dressing observation.
 - Complication prevention: Instruct on preventing postoperative wound infections, deep vein thrombosis, and constipation.
 - Postoperative life precautions: Inform on prohibited movements, allowed actions, and mobility techniques.

5. Data collection

Data collection will be conducted at five time points: on admission day (baseline, T0), surgery day (preoperative) (T1), one week post-surgery (T2),

two weeks post-surgery (T3), and four weeks post-surgery (T4). The collected study data will include demographic and clinical information collected by the principal investigator (recruiter), as well as outcome measures collected by assessors from T0 through T4. These outcome indicators encompass knee osteoarthritis severity, exercise adherence, self-efficacy, knee joint function, knee range of motion, and pain intensity.

6. Outcome assessment

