6.2. Secondary outcomes

The secondary outcomes are changes from baseline in exercise adherence, self-efficacy, knee joint function, knee range of motion, and pain intensity at T1, T2, T3, and T4, as well as changes from baseline in knee osteoarthritis severity at T2, T3, and T4.

Exercise adherence will be measured using the Orthopaedic Patient Functional Exercise Compliance Scale developed by Chinese scholars (Tan et al., 2019). This instrument effectively assesses rehabilitation adherence among orthopaedic patients. It consists of 15 items covering three dimensions—physical exercise adherence, psychological exercise adherence, and active learning exercise adherence—with patients rating their ability to perform each activity. Each item is rated on a five-point Likert scale ranging from 1 (“Not at all possible”) to 5 (“Completely possible”). Total scores range from 15 to 75, with higher scores reflecting greater adherence to rehabilitation exercises.

Self-efficacy will be measured using the Chinese version of the Self-Efficacy for Rehabilitation Scale (SER) (Wang et al., 2014). This scale has demonstrated strong reliability and validity in assessing rehabilitation self-efficacy among patients undergoing knee replacement. The Chinese version of the Self-Efficacy for Rehabilitation Scale includes two dimensions—Rehabilitation Self-Efficacy (five items) and Coping Self-Efficacy (seven items)—for a total of 12 items. Each item is rated on an 11-point Likert scale ranging from 0 (“Not at all”) to 10 (“No difficulty whatsoever”), yielding a maximum total score of 120. Higher scores denote greater rehabilitation self-efficacy.

Knee joint function will be measured using the Hospital for Special Surgery (HSS) Knee Scoring System (Weitzel et al., 2002). This 100-point scoring system includes pain (30 points), function (22 points), range of motion (18 points, one point per eight degrees), muscle strength (10 points), flexion

deformity (10 points), and stability (10 points). Points are deducted if patients use walking aids or present with flexion contracture or varus/valgus deformities. Total scores range from 0 to 100, with higher values reflecting superior knee joint function.

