The Clinical Research Management Department and the Ethics Committee of the study-conducting hospital will oversee trial implementation and ensure compliance with ethical standards. The principal researcher is required to submit regular progress reports and interim results to the Clinical Research Management Department and the Ethics Committee of the study-conducting hospital. They will review the completeness, accuracy, and timeliness of data collection, as well as procedures related to participant enrolment, informed consent, eligibility assessment, and protocol adherence. Based on the findings of interim reports and a comprehensive evaluation of the study's efficacy, safety, and feasibility, they will make the final determination regarding whether the trial should be terminated.

9. Ethical

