9.1. Research ethical approval and informed consent

This study adheres to the ethical principles outlined in the Declaration of Helsinki and has received approval from the Ethics Committee of the research implementation hospital (No. KY-2025-105). All participants will receive written information detailing the study objectives, procedures, potential risks, and benefits. Participation in the study is entirely voluntary, and participants may

withdraw at any time without providing a reason or facing any consequences. Each participant must sign a written informed consent form before enrolment. Participants will withdraw from the study under the following circumstances: withdrawal of consent, loss to follow-up, receipt of unapproved rehabilitation or treatment during the study period, or a clinician's determination that the participant is unsuitable to continue, such as in cases of serious adverse events or serious complications.

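### Safety is a stated ground for terminating the trial, but the plan collects, analyses and reports no adverse events in either arm

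*Combined protocol and SAP*

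**What the plan says.** Section 8 gives oversight to two hospital bodies, the research management department and the ethics committee. On what they receive it says: "The principal researcher is required to submit regular progress reports and interim results". On what they decide, it says that after weighing "efficacy, safety, and feasibility, they will make the final determination regarding whether the trial should be terminated". The items it lists for review are data quality and the conduct of enrolment, consent, eligibility and protocol adherence.

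Section 5 sets out the data. The recruiter gathers demographic and clinical information, and the assessor gathers the outcomes at T0 to T4: "These outcome indicators encompass knee osteoarthritis severity, exercise adherence, self-efficacy, knee joint function, knee range of motion, and pain intensity". Section 6.2 matches this: "The secondary outcomes are changes from baseline in exercise adherence, self-efficacy, knee joint function, knee range of motion, and pain intensity", together with WOMAC at the later visits. Section 7 describes no safety analysis.

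Adverse events are named once, in section 9.1, where a clinician may find a participant unsuitable to continue, "such as in cases of serious adverse events or serious complications".

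Preoperative contact differs by arm. In section 4.2.2, "navigators conducted daily ward visits to provide face-to-face exercise guidance, including two 20-minute supervised sessions per day". For controls, section 4.1.2 says: "They were also advised to promptly inform ward medical staff of any unusual conditions or concerns".

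**The concern.** A stated input to the termination decision has no planned source. If the protocol is followed as written, the two bodies are asked to evaluate safety, but nobody is assigned to ask about, record, define or tabulate events. The final report could not give harms by arm either. The trial enrols surgical patients up to 90 years old (section 2.1), and its own navigator material covers falls, wound infection and deep vein thrombosis (section 4.2.2, theme vii).

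There is a secondary issue of ascertainment. Without a common method, what becomes known depends on who is looking. Before surgery the experimental arm has scheduled one-to-one contact, while controls are asked to come forward themselves. A comparison built afterwards from informally noticed events would not be on an equal footing.

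**Working it through.** The plan gives no adverse event rate, safety boundary or safety figure, so there is none to reproduce. The check is mainly a reading of the sections side by side.

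**1. Is there any planned source of event data?**

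- *Section 5, outcomes:* six measures, none an adverse event.
- *Section 5, clinical information:* undefined. Section 3 places demographic and clinical data collection before the allocation envelope is opened, so it cannot be assumed to capture later events.
- *Section 6:* WOMAC, HSS, range of motion and VAS would partly reflect a pain flare or loss of function. They do not record a fall, a thrombosis, a wound infection or a postponed operation.
- *Section 7:* no safety analysis.
- *Section 8:* progress reports and interim results of unspecified content. The listed review items do not include events.
- *Section 9.1:* one mention of serious adverse events, as an example behind a clinician's judgement. There is no definition, form, reporting route or tabulation.
- *Section 9.2:* case report forms exist, but their content is not described.

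What remains is pain and function scores plus withdrawals known to the team. None of this is a planned event record.

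**2. How different is preoperative contact?**

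Inputs: two supervised sessions a day (section 4.2.2); an admission-to-surgery interval of 3 to 7 days (section 2.1, exclusion iv).

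Sessions per experimental participant: 2 × 3 = 6 to 2 × 7 = 14. Controls have no supervised sessions planned, though they are inpatients and receive an explanation on admission. These figures count exercise sessions. They do not measure how well harms are detected. No navigator contact is described after surgery, and one blinded assessor sees both arms from T0 to T4 (section 3).

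**3. What would a detection gap do?**

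This is an illustration. Only the arm size of 42 (section 2.2) comes from the documents. Assumed: the same true preoperative harm rate in both arms, 10%, and detection of 0.9 in the navigator arm.

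Recorded events per arm = 42 × true rate × detection. Navigator arm: 42 × 0.10 × 0.9 = 3.8. Navigator share = 0.9 / (0.9 + control detection), which does not depend on the true rate.

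| Assumed control detection | Recorded, navigator | Recorded, control | Navigator share |
|---|---|---|---|
| 0.9 | 3.8 | 3.8 | 50% |
| 0.7 | 3.8 | 2.9 | 56% |
| 0.5 | 3.8 | 2.1 | 64% |
| 0.3 | 3.8 | 1.3 | 75% |

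Any gap in this direction tilts the counts, but a large majority in the navigator arm requires control detection of about half the navigator arm's or lower. The documents do not say where in this range the trial would fall.

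**The case against.** The strongest reply is that safety information would not be wholly absent. Pain and function are measured in both arms, withdrawals after serious events would be known, clinicians see inpatients in both arms, and the unseen case report forms might have room for events. This has some force: it would be wrong to say that the bodies have no information at all. It does not close the gap, because the protocol gives no route from ward notes or withdrawal reasons to the trial data or the interim reports.

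On ascertainment, a reader might infer more than the documents support: that harms would surface mostly in the navigator arm, that this arm would look less safe, or that it would lose more participants to withdrawal. Four points stand against this:

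- Unequal contact is documented only for the 3 to 7 preoperative days, while follow-up runs to four weeks after surgery. Wound problems, and much of the thrombosis risk, belong to the later period.
- No section says that navigators record harms.
- Controls are inpatients who are told to speak up promptly.
- Under section 9.1 the judgement that a participant is unsuitable to continue rests with a clinician, not the navigator.

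The navigator's teaching on abnormal symptoms and wound observation might affect self-reporting after discharge, but that too is conjecture. What survives is that preoperative events may come to light more readily in the navigator arm.

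**Conclusion.** The concern holds for the missing event data. Safety is named as a ground for termination, yet no adverse event collection, outcome, analysis or report is specified. This goes beyond missing detail, because the plan relies on an input that it does not gather. The conclusion rests on the text alone and needs no numerical assumption; it would change only if an undisclosed form or procedure already covers events.

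The ascertainment point holds only as a possibility, limited to the preoperative days, with a direction but no known size. The table above shows a range under assumed detection rates and is not an estimate.

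The primary WOMAC comparison from T0 to T1 is not put in doubt. What is affected is the safety part of oversight and any report of harms by arm. The change should be made, but the trial's main question does not depend on it.

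**What to change.** 1. Add adverse events to the section 5 data list, with short definitions: for example falls, pain flare, thrombosis, wound problems and postponed surgery.
2. Have the existing blinded assessor ask one identical, neutrally worded checklist in both arms at T1, T2, T3 and T4.
3. Add counts by coded group to the progress reports in section 8, and say there that the safety evaluation draws on them. Add a descriptive table by arm to section 7.

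The cost is about one case report form page and slightly longer assessments, with no new visits or staff. There is also a small risk to blinding: asking about events, above all pain during exercise, may prompt a participant to mention the navigator, and section 3 relies on participants not disclosing their group. Neutral wording, asking the checklist after the outcome measures, and repeating the non-disclosure instruction reduce that risk.

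The gain in precision is modest. With complete collection, no events of a given type among 42 participants would give a one-sided 95% upper bound of 1 − 0.05^(1/42) = 6.9%. With 33 followed, the section 2.2 figure before the attrition allowance, it is 1 − 0.05^(1/33) = 8.7%. These bounds describe what the amended trial could say about harms; they do not measure the present gap.

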9.1. Research ethical approval and informed consent

This study adheres to the ethical principles outlined in the Declaration of Helsinki and has received approval from the Ethics Committee of the research implementation hospital (No. KY-2025-105). All participants will receive written information detailing the study objectives, procedures, potential risks, and benefits. Participation in the study is entirely voluntary, and participants may

withdraw at any time without providing a reason or facing any consequences. Each participant must sign a written informed consent form before enrolment. Participants will withdraw from the study under the following circumstances: withdrawal of consent, loss to follow-up, receipt of unapproved rehabilitation or treatment during the study period, or a clinician's determination that the participant is unsuitable to continue, such as in cases of serious adverse events or serious complications.

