2.1. Participant selection criteria

Inclusion Criteria: (i) patients diagnosed with knee osteoarthritis who are undergoing primary unilateral total knee arthroplasty; (ii) aged between 45 and 90 years; (iii) assessed by the attending physician as having sufficient physical capacity to tolerate preoperative rehabilitation exercises and adequate communication skills to cooperate with all examinations and assessments; and (iv) informed consent was obtained from the patient, and the signed informed consent form was duly completed.

Exclusion Criteria: (i) patients who are uncooperative due to impaired consciousness, cognitive dysfunction, or other factors; (ii) presence of severe concurrent comorbidities, including liver cirrhosis, respiratory failure, renal failure, malignancy, or trauma; (iii) a history of significant neuromuscular disorders or other joint diseases, as determined by the attending physician, that impair knee joint function; (iv) a time interval of greater than 7 days or less than 3 days between the admission day date and the scheduled surgery date; and (v) patients who have undergone systematic lower limb functional training within the past four weeks.

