- ③ Perioperative care guidance: Including preoperative daily life precautions, management of perioperative pain, respiratory care, postoperative lower limb thrombosis prevention, and preparation of surgical supplies.

(iii) Assess participant needs and facilitate access to resources:

- ① Needs assessment: Navigators will understand participants' illness conditions, prior treatment histories, and current physical states and will discuss expectations regarding the surgery with participants, which includes pain management, functional recovery, and quality-of-life improvements, alongside anticipated post-operative rehabilitation requirements such as physiotherapy, independence in activities of daily living, and care support.
- ② Resource linkage: Based on the needs assessment, the navigator

will introduce available hospital resources to participants, such as rehabilitation and pain management teams, the hospital's psychological counseling centre, and continuing care services.

- ③ Information provision and assistance: The navigator will explain the surgical procedure, post-operative precautions, and expected recovery timeline in detail according to the participant's needs, ensuring they understand each step. Information on hospital companion services will be provided, including details of companions, contact information, service content, and fees. Offer medical insurance reimbursement details, with navigators explaining coverage scope, claim procedures, and consultation channels for different insurance schemes. Additionally, navigators will assist with scheduling appointments for specialised examinations or treatments.
- ④ Reminder services: Navigators will provide reminders for scheduled preoperative examinations, including advance notification of any special requirements (e.g., fasting, holding urine). Navigators will also offer weather-related reminders and guidance as appropriate.

(iv) Offer social and emotional support:

- ① Provide encouragement and support: During preoperative rehabilitation exercises, navigators offer positive feedback and encouragement to help participants build confidence and overcome psychological barriers. Sharing video testimonials of successful recovery cases inspires participants' motivation to exercise; using quantifiable metrics (such as scales) to document progress enables participants to perceive the effects of rehabilitation.

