6.1. Primary outcome

The primary outcome is the change in knee osteoarthritis severity from admission day (baseline, T0) to surgery day (preoperative) (T1). As the intervention in this study aims to enhance patient adherence to preoperative rehabilitation exercises, the ultimate objective is to improve their rehabilitation outcomes. Therefore, the change in knee osteoarthritis severity from T0 to T1 in both groups of participants will be used to evaluate the effectiveness of the intervention.

Knee osteoarthritis severity will be measured using the Chinese version of the Western Ontario and McMaster Universities Osteoarthritis Index (WOMAC) Scale, which is a self-administered instrument specifically developed to assess the severity of knee osteoarthritis and the efficacy of related treatments (Bellamy et al., 1988). The scale consists of 24 items divided into three subscales: pain (5 items), stiffness (2 items), and physical function (17 items). Several scoring methods have been developed for the Western Ontario and McMaster Universities Osteoarthritis Index Scale items (Noyes, 2016). In this study, a 5-point Likert scale is employed, where 0 represents “no difficulty” and 4 represents “extreme difficulty”. The total score ranges from 0 to 96, with higher scores reflecting more severe knee osteoarthritis.

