Knee range of motion (ROM) will be measured with a goniometer. ROM measurement assesses knee movement amplitude, serving as a critical indicator of knee joint function and a key indicator for evaluating rehabilitation outcomes following total knee arthroplasty. Normal knee range of motion values are as follows: flexion, 0°–135°; extension, 0° (some individuals may exhibit hyperextension of 0°–10°); active range, 0°–135°; and passive range, up to 150°.

Pain intensity will be measured using the Visual Analogue Scale (VAS). The VAS consists of a 10-centimetre horizontal line divided into 10 equal intervals, where higher scores represent greater pain intensity. A score of 0 denotes no pain, whereas a score of 10 denotes the most severe pain imaginable. Patients are instructed to mark the point on the line corresponding to their perceived pain intensity.

7. Statistical analysis

IBM® SPSS Statistics 27.0 will be used to analyse the data from all randomised participants. Statistical significance was set at $p \leq 0.05$. Categorical variables (e.g., gender, marital status, payment type) appeared as frequencies and percentages. Continuous variables (e.g., age, height, weight) appeared as mean \pm standard deviation (SD). Continuous data meeting the assumptions of normality and homogeneity of variance were analysed using independent-sample t-tests; otherwise, the Wilcoxon signed-rank test appeared. Categorical data were analysed using the chi-square test or Fisher's exact test for intergroup comparisons. Generalised Estimating

Equations (GEE) were employed to compare longitudinal changes in outcome variables between groups, with statistical significance set at $p < 0.05$ (two-tailed). The GEE was chosen as it accounts for within-subject correlations inherent in repeated measures, thereby improving the efficiency of parameter estimation in longitudinal analyses. Moreover, the GEE approach flexibly accommodates missing data. When the proportion of missing data was below 5%, the GEE inherently accommodated the missing values; otherwise, multiple imputation procedures were applied.

8. Trial monitoring

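### Section 9.1 ends follow-up, not only the programme, after unapproved care or a clinician's decision, creating avoidable missing outcomes

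*Combined protocol and SAP*

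**What the plan says.** Section 9.1 opens its list with "Participants will withdraw from the study under the following circumstances" and gives four reasons: withdrawal of consent, loss to follow-up, "receipt of unapproved rehabilitation or treatment during the study period", and a clinician's finding that the participant is "unsuitable to continue, such as in cases of serious adverse events or serious complications". All four carry the same consequence.

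Section 5 schedules assessments at T0 (admission), T1 (surgery day, before the operation), and T2, T3 and T4 (one, two and four weeks after surgery). It does not mention participants who deviate or stop. Under Section 4.2 the navigator's programme runs from admission to surgery.

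Section 7 states that SPSS "will be used to analyse the data from all randomised participants". Below 5% missing data the GEE is used as it stands; otherwise multiple imputation is applied. No sensitivity analysis for missing data is given.

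No section defines unapproved rehabilitation or treatment. In the experimental arm (Section 4.2) the navigator "will introduce available hospital resources to participants, such as rehabilitation and pain management teams", and "navigators will assist with scheduling appointments for specialised examinations or treatments".

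**The concern.** The first two reasons in Section 9.1 can make data unobtainable. The other two are events after randomisation, and many of the participants concerned could still be assessed. Treating all four alike discards outcomes that could have been collected, from participants whose extra treatment or complications may well be related to those outcomes.

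Data from before withdrawal can still enter the GEE. Later values would rest wholly on missing-data assumptions, so the commitment to analyse everyone randomised would be met only in part.

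The undefined term could also operate unevenly. Experimental participants are introduced to rehabilitation and pain management teams as part of their assigned arm. A control participant who reached the same services alone might be classed as having received unapproved care. The plan does not say.

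**Working it through.** **Does withdrawal mean leaving follow-up?** Section 9.1 speaks of the study, not the programme. After T1 no assigned programme remains to stop, so a withdrawal between surgery and T4 can only remove later assessments. Sections 5 and 7 restore none of them.

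**Which outcomes are exposed?**

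- *Primary (Section 6.1, change in WOMAC from T0 to T1).* Section 2.1 excludes patients with "a time interval of greater than 7 days or less than 3 days between the admission day date and the scheduled surgery date", which leaves a window of 3–7 days. Only unapproved care or clinical events in that window matter. Complications of surgery come too late.
- *Secondary (Section 6.2, T2–T4).* Someone withdrawn in the first postoperative week, before T2, loses three of the four post-baseline assessments.

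**Plan figures.** Section 2.2 allows 20% attrition: 33/(1 − 0.20) = 41.25, rounded up to 42 per group, 84 in total. Then 0.20 × 84 = 16.8, about 17 participants, not divided by reason. No rate is given for either kind of withdrawal at issue.

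**Illustration.** Assumptions: outcome SD of 1, an independence working correlation (Section 7 names none), nothing recovered from earlier visits, and the 5% rule counted by participant.

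If a proportion *f* of an arm is removed, and those removed differ from those retained by *g* SD, the retained mean differs from the full-arm mean by *f* × *g*. The bias in the treatment difference is *f* × *g* in one arm minus the same product in the other.

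Threshold: 4/84 = 4.8%, so no imputation; 5/84 = 6.0%, so imputation.

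Four removed, all from one arm:

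- *f* = 4/42 = 0.095 against 0
- bias = 0.095 × 0.5 = 0.048 SD, to 0.095 × 1.0 = 0.095 SD
- SE = √(1/42 + 1/38) = 0.224 SD
- bias/SE = 0.21 to 0.43
- two-sided rejection under no effect, Φ(−1.96 + b) + Φ(−1.96 − b) with b = bias/SE: 0.055 to 0.071

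Other splits of four:

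| Split | Bias (SD) | False-positive rate |
|---|---|---|
| 4 vs 0 | 0.048–0.095 | 5.5–7.1% |
| 3 vs 1 | (2/42) × 0.5 to (2/42) × 1.0 = 0.024–0.048 | 5.1–5.5% |
| 2 vs 2, equal gap | 0 | 5% |

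For 3 vs 1, SE = √(1/39 + 1/41) = 0.224 SD and b = 0.11 to 0.21.

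**If the 5% is counted by assessment.** Section 7 gives no unit. With 84 × 5 = 420 planned assessments and three lost per withdrawal, five withdrawals give 15/420 = 3.6%, six give 18/420 = 4.3%, and seven give 21/420 = 5.0%. Imputation would then start only at seven.

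**The case against.** The strongest reply is that little of consequence is at risk. The primary outcome is measured over a few days in hospital, and what remains is secondary, with unknown size and direction. This stands as a limit on the finding.

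The illustration is also a chosen one. It takes the largest count that escapes imputation and puts every case in one arm. With equal risk in both arms, a 4–0 split in either direction has probability 2 × (42·41·40·39)/(84·83·82·81) = 0.12, and no section shows that the risks differ. The 3 vs 1 split makes almost no difference to the error rate. At the 20% attrition the plan allows for, multiple imputation would apply, and it can remove whatever part of the gap earlier data predict. All of this is fair. The figures are upper illustrations for their inputs, not estimates. Imputation cannot, however, remove a difference that earlier data do not predict, and the attrition allowance protects precision rather than against bias.

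The uneven reading of unapproved is conjecture. A control inpatient using the same hospital's services might never be classed that way, and Section 4.1 tells controls to raise concerns with ward staff. What stands is that the term is undefined.

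Finally, some participants removed after serious events could not attend anyway, and a per-protocol or missing-not-at-random analysis goes further than the wording gap requires. Both points are accepted: the core remedy is continued assessment where feasible, and the extra analyses are secondary.

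**Conclusion.** The concern holds and should be fixed. Section 9.1 as written turns two post-randomisation events into loss of follow-up, and no other section restores the assessments. Confidence in this reading is high; the size and direction of any bias are unknown.

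The effect falls mainly on the T2–T4 secondary outcomes, with limited preoperative exposure of the primary outcome. Under the stated assumptions the distortion ranges from nil to 0.095 SD, or up to 0.4 standard errors. It is nil if those removed resemble those retained, or if rate times gap is equal in the two arms. The case does not depend on a large bias: the loss comes from the protocol's wording and can be avoided at visits already scheduled.

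**What to change.** **Section 9.1.** Separate stopping the assigned programme from leaving follow-up. End data collection only for withdrawal of consent to follow-up or true loss to follow-up. In all other cases keep the remaining T1–T4 assessments where the participant is willing and able, record the event and its date, and analyse the participant in the randomised arm.

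**Sections 9.1 and 4.2.** Reconcile the two so that unapproved has one written meaning, applied in both arms. What that meaning should be is for the investigators.

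**Section 7 (secondary).** State that data collected after such events are used, and make exclusion of these participants a per-protocol sensitivity analysis. For outcomes still missing, add a missing-not-at-random analysis, for example imputed values shifted by 0 to 1 SD separately by arm, reporting where the conclusion changes. The 0–1 SD range is a suggestion and has no source in the documents. State also whether the 5% is counted by participant or by assessment.

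**Cost.** Wording in Sections 9.1, 4.2 and 7, a few more assessments at visits already scheduled, and a little more analysis. Decisions about stopping the programme are unchanged.
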